## **VII.E. Project Description (E)**

**VII.E.1** *Will subjects be randomized?*  
No

**VII.E.3** *Will any questionnaires, surveys, or written assessments be used to obtain data directly from subjects in this study?*  
Yes

**VII.E.4** *List all questionnaires, surveys, written assessments and ATTACH each one to the application. (NOTE: You are NOT prohibited from attaching copyrighted materials to this application)*  
202010229\_ScreeningQuestionnaire\_v1  
202010229\_PreScreeningQuestionnaire\_v1  
202010229\_DataCollectionSheets\_v1.docx  
202010229\_Emailfollowupscript\_v1.docx

**VII.E.5** *Does this project involve creating any audiotapes, videotapes, or photographs?*  
No

**VII.E.6** *Provide a detailed description in sequential order of the study procedures following the consent process - DO NOT cut and paste from the Consent Document.*

*Describe study populations separately if they will be participating in different procedures - include CONTROL population if*

*applicable.*

**DESCRIBE:**

- *What subjects will be asked to do/what happens in the study (in sequential order)*
- *The time period over which procedures will occur*
- *The time commitment for the subject for individual visits/procedures*
- *Long-term followup and how it occurs*

Following consent, the subject will fill out a questionnaire collecting information about demographic information age, race/ethnicity, sex assigned at birth, current medications and ongoing medical conditions. The subject will be asked to elaborate on the duration and severity of medical conditions and any treatments received. No medical records will be consulted to obtain or confirm this information. A member of the research team will use this information to screen out subjects meeting any of the exclusion criteria defined in VI.13. Subjects who pass the screening may proceed to the next step described below. Subjects should allow for both in person and electronic consent and screening procedures to take approximately 1 hour; whenever possible, if in person, this will be done on the same day as when the subject starts the study procedures.

On Day 0 (may be the same day as consent is obtained), the subject will sit in the study room at the College of Pharmacy for 30 minutes prior to any procedures. This allows the subject's skin to acclimate to the ambient environment in the study room (temperature, humidity). During this 30 minute period, the study team member will verify screening information collected through the online survey with the participant, as well as measure height, weight, calculate BMI. If screening information is verified correct from participant research procedures will continue as planned. (This procedure will be followed as do to scheduling constraints it is possible that some time has passed from when the subject consented to when they are scheduled to complete their study procedures. Verifying this information will help us determine if their original answers remain accurate and their eligibility remains.) If participants answers indicate that they are actually ineligible to continue their participation no further procedure will take place and the subject will be removed from the study. Following this acclimation, the researcher will identify and mark with a pen 3 sites each on the upper arm, forearm, and the palm. Hair may be clipped (but not shaved) at any sites if necessary. Noninvasive baseline measurements will be taken at each of the 9 sites as follows:

- Transepidermal water loss (TEWL) will be measured by resting a probe gently against the skin. This measurement will take 1-3 minutes at each site. (TEWL will only be measured on Day 0)
- Electrical resistance (impedance) will be measured with an impedance meter by applying gel electrodes to each site and a reference electrode at a nearby site. The measurement will be repeated 3 times at each site, and will take less than 2 minutes total at each site.
- Skin color and redness will be measured by placing a colorimetry probe gently against each site. This measurement will take less than 30 seconds at each site.
- Dynamic-OCT will be used to obtain an image of the skin by holding a probe lightly on the skin. This measurement will take about 30 seconds at each site. Microvasculature density, epidermis thickness, and epidermal junction depth can be measured using a single scan.

Following baseline measurements on Day 0, micropatches (an adhesive microneedle patch) will be applied to two of the three identified sites at each anatomical location. The sites will first be cleansed with an alcohol swab. A sterilized micropatch

containing 50 tiny projections, each 800 um in length, will be placed perpendicular to the skin, and the researcher will apply gentle pressure to the back of the patch for 15 seconds. A new micropatch will be used for each site, and the micropatches will be discarded immediately after use. Micropatch application will only occur on Day 0. Immediately after treating a site with a micropatch, TEWL, OCT and impedance measurements will be repeated. One of the micropatch sites at each location will be covered with a sterile occlusive covering following micropatch application; this will be secured to the skin using medical tape such as Tegaderm or Bioclusive tape. The second micropatch application site at each location will not be covered. The third site at each location will not receive micropatch application, but will simply be covered with an occlusive covering. This serves as a control for the effect of occlusion alone on normal skin. Day 0 procedures will require 3 - 3.5 hours in total.

Subjects will be asked to return to the College of Pharmacy every 24 hours for the next 2 days. On each day the occlusive coverings will be removed and the OCT and impedance measurements will be repeated at all sites. Fresh occlusive coverings will be applied after measurements have been completed. Procedures on days 1 and 2 will require approximately 2 – 2.5 hrs.

On Day 2 (the final day), the occlusive coverings will be removed and not replaced. Within 3-6 days after the Day 2 visit (or the last completed visit if a participant decides to drop out early) a study team member will contact the subject via phone or email to determine if the subject is experiencing any redness or irritation at any of the measurement sites. No long-term follow-up will be necessary. The overall time commitment for this study is 7 - 10 hours in one week, across 3 – 4 study days if consent is obtained on a different day than the study start day.

To summarize, the 9 sites will receive the following measurements and treatments:

Palm: sites 1 – 3

Site 1: Micropatch application + occlusive covering

Site 2: Micropatch application, no occlusive covering

Site 3: Occlusive covering, no micropatch application

Forearm: sites 4 – 6

Site 4: Micropatch application + occlusive covering

Site 5: Micropatch application, no occlusive covering

Site 6: Occlusive covering, no micropatch application

Upper arm: sites 7 – 9

Site 7: Micropatch application + occlusive covering

Site 8: Micropatch application, no occlusive covering

Site 9: Occlusive covering, no micropatch application

Measurements of TEWL, Dynamic-OCT, colorimetry, and impedance will be made at baseline (Day 0) for all sites. TEWL, Dynamic-OCT, and impedance measurements will be repeated immediately after micropatch application. Dynamic-OCT and impedance measurements will be measured at all sites on days 1 and 2.

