**VII.D.29 *Provide a description of the enrollment and consent process for adult subjects***

- **Describe each study population separately including control population**
- **Include when recruitment and consent materials are used**
- **Use 3rd person active voice “The Principal Investigator will identify subjects. For example, the principal investigator will identify potential subjects, the study coordinator will discuss the study with subjects over the telephone and schedule the first study visit, etc...”**
- **Describe the steps that will be taken by the research team to minimize the possibility of coercion or undue influence during the consent process**

Participants in this study will be normal healthy individuals aged 18-45. All participants will act as their own controls.

This study will be advertised through the University of Iowa campus-wide email system and through the University of Iowa Health Care “Noon News,” a daily announcement flier for community and faculty members within the UIHC. Advertisements for this study have been created so that specific subject populations may be better reached via targeted advertisements, in order to meet our enrollment goals. (attached docs: 202010229\_MassEmail\_v1; 202010229\_NoonNews\_v1)

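### Treatments follow a fixed site list with no random or rotated assignment and no record of position, so comparisons with the control sites may carry position or operator-choice effects that the site baselines do not remove

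*Combined protocol and SAP*

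**What the plan says.** In VII.E.6, on Day 0, "the researcher will identify and mark with a pen 3 sites each on the upper arm, forearm, and the palm". Baseline TEWL, impedance, colorimetry and OCT are then taken at all nine sites. After that, micropatches "will be applied to two of the three identified sites at each anatomical location", with no rule for which two.

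The closing summary of VII.E.6 lists for the palm "Site 1: Micropatch application + occlusive covering", then "Site 2: Micropatch application, no occlusive covering", then "Site 3: Occlusive covering, no micropatch application". The same order repeats for the forearm (sites 4 to 6) and the upper arm (sites 7 to 9).

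VII.E.1 asks "Will subjects be randomized" and is answered no. That question concerns subjects, but no random or rotated assignment of sites appears elsewhere either. No passage says which physical position a site number denotes.

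Comparison between sites is part of the design. I.4 describes two of the three sites at each location as controls. VII.E.6 says of the occlusion-only site: "This serves as a control for the effect of occlusion alone on normal skin". VII.D.29 states: "All participants will act as their own controls".

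XI.1 plans pre/post paired t-tests at each site, a micropore closure half-life, and one-way ANOVAs by skin color and race/ethnicity. It names no test between the three treatment sites.

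**The concern.** Within-subject controls are informative only if the spot that receives each treatment is chosen without regard to how that spot will respond. The plan gives no such protection on either reading of the site numbers.

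- **Numbers as fixed positions.** Each treatment then sits in the same place in every subject. A position that takes the microneedles differently, or closes faster, looks like a treatment effect.
- **Numbers as treatment labels only.** The researcher, who knows the treatments, then decides which marked spot gets which. The sequence in VII.E.6 allows this choice after the baseline readings have been seen. Choosing on baseline values can induce regression to the mean, which simple change scores do not remove.

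At stake are the comparison of occluded with uncovered micropatch sites, and of micropatch with occlusion-only sites. A systematic effect of this kind does not shrink as subjects are added. If position is not recorded, later analysis cannot separate it from treatment.

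**Working it through.** The plan states no power or error-rate figure on this point (XI.2 declines a power analysis), so there is none to reproduce. Three checks follow.

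**1. Can treatment and position be separated?** Take one location and 100 subjects (VI.1). The design matrix has 100 subject columns, 2 treatment contrasts and 2 position contrasts: 100 + 2 + 2 = 104 columns.
- Fixed list, with numbers read as positions: rank 102. Both position contrasts coincide with the two treatment contrasts.
- Three-sequence Latin square, or all six orders: rank 104. Both sets of effects can be estimated.

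**2. What do the site baselines remove?** This simulation compares two adjacent sites with no true treatment difference, 20 subjects (the target per group in XI.2), a two-sided paired t-test at 0.05 and 1,000 runs. The measurement SD of 0.7 and the position effects (units per step) are assumptions.

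| Position effect, fixed layout | Analysis | Bias | False positives |
|---|---|---|---|
| 0.5 on level only | raw post-treatment value | 0.50 | 57% |
| 0.5 on level only | change from baseline | -0.01 | 6% |
| 0.25 on response | change from baseline | 0.24 | 10% |
| 0.5 on response | change from baseline | 0.51 | 34% |

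An analytic check agrees within simulation error. The SE of the change contrast is 0.7 × sqrt(4) / sqrt(20) = 0.313. The ratios 0.25/0.313 = 0.80 and 0.5/0.313 = 1.60 give rejection rates of about 12% and 33% from the noncentral t. With a random draw from the six orders, bias in the change contrast was between -0.013 and 0.004, with false positives of 4.5% to 6.1%.

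Baselines therefore remove a stable level difference but not an effect on the response. Closure half-life has no pre-treatment value, so nothing can be subtracted from it.

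**3. Illustration at full enrolment.** Inputs: n = 100 (VI.1). The within-subject correlation rho and the position effect d, in SD units, are assumed. SE = sqrt(2(1 - rho)/100). The two-sided rejection probability is P(Z > 1.96 - d/SE) + P(Z < -1.96 - d/SE).

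| rho | SE | d = 0.1 | d = 0.2 | d = 0.3 |
|---|---|---|---|---|
| 0.3 | 0.118 | 13.5% | 39% | 72% |
| 0.5 | 0.100 | 17% | 52% | 85% |
| 0.7 | 0.077 | 25% | 73% | 97% |

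Here d is only the part of a position effect that survives into the contrast analysed. For a stable level difference analysed as change from baseline, d is 0 and the rate stays at 5%.

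**The case against.** A reader might infer that every position effect is fully confounded with treatment and that the planned tests are therefore unsafe. The documents do not support that, for these reasons.

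- All nine sites are measured before treatment, so a stable difference between neighbouring spots cancels in change from baseline. This stands. However, XI.1 does not commit any between-site comparison to change from baseline, and it cannot apply to half-life.
- Nothing says that site numbers are positions. The narrative in VII.E.6 can be read as naming sites by treatment. Complete aliasing needs the positional reading; otherwise confounding is possible but not complete. This stands, though it replaces a fixed layout with an unstated selection rule.
- XI.1 plans no between-site test. Its paired tests stay within one site. All subjects share one list, so a constant position effect cancels in the race/ethnicity ANOVAs. This stands unless the effect differs by group, which the documents neither suggest nor exclude.
- The occlusion-only site's change from its own baseline addresses occlusion on normal skin without a neighbour. This is also fair. But I.4 presents the control sites as companions to the occluded micropatch site, and that use requires comparing them.
- A false-positive rate under no micropatch effect is of limited interest, since the study presumes that microneedles make pores. The occlusion comparison is the more exposed of the two.

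**Conclusion.** The point holds in limited form. The plan describes no random or counterbalanced assignment of treatments to positions and no record of position. Comparisons with the control sites can therefore be confounded with position or operator choice, to the extent that these affect the response to the micropatch or the closure half-life. Stable level differences are handled by the site baselines. The planned within-site tests and group ANOVAs are largely unaffected unless a position effect varies by group.

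The size is unknown. The 17%, 52% and 85% figures are illustrative: they rest on assumed effects and correlations, and concern a contrast outside the formal analysis. They should not be read as the error rate of any planned test. This is a cheap design improvement, and nothing here invalidates the stated analyses. Pilot status does not remove the case for it, because a larger sample would not cure the bias.

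**What to change.** In VII.E.6:

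1. Define the three positions at each location (for example by a simple map).
2. Assign the three treatments to positions, per subject and per location, from a pre-generated random-permutation or Latin-square list balanced within race/ethnicity group. With 20 per group, three sequences split 7, 7 and 6.
3. Open the assignment only after the sites are marked.
4. Record position on the data sheet.

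In XI.1, state that any between-site comparison will use change from baseline (or half-life, where that is the outcome) with position as a term in the model.

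The cost is a printed list, one extra data field and a small risk of allocation slips. No extra subjects, visits or measurements are needed.

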## VII.E.7

***Will you attempt to recontact subjects who are lost to follow-up?***

No - those lost to followup will not be recontacted

**VII.E.9**      *Will subjects be provided any compensation for participating in this study?*  
Yes

**VII.E.10**      *Cash*  
No

**VII.E.11**      *Gift Card*  
No

**VII.E.12**      *Check*  
No

**VII.E.16**      *Other*  
Yes

**VII.E.17**      *Describe:*  
Parking passes will be supplied for the subjects to park in the University ramps near the College of Pharmacy building.

The evoucher system will be used to compensate the subjects for their research study visit completion.

**VII.E.18**      *If you plan to compensate subjects using cash, checks or cash equivalent does your unit have a [Cash Handling Procedure](#) in place that has been approved by Accounting Services?*  
Yes

**VII.E.19**      *Describe the compensation plan including*

- *Compensation amount and type per visit*
- *Total compensation*
- *Pro-rating for early withdrawal from study*

Subjects will be compensated \$175 according to the following schedule:

Day 0 \$75

Day 1 \$50

Day 2 \$50

Total \$175

Compensation will be prorated for any subject who does not complete all days of the study. Subjects will only be paid for

the study days whey complete. Subjects will be paid in one check. Subject's who park in the University of Iowa ramps will be supplied with parking vouchers.

## **VIII. Risks**

### **VIII.1**

*What are the risks to subjects including*

- emotional or psychological*
- financial*
- legal or social*
- physical?*

In general, micropatch treatments are well tolerated. However, the skin could become irritated or inflamed from the microneedle insertion or from the adhesives (either on the micropatches, the impedance electrodes used to make measurements, or the medical tape used to hold the occlusive patches in place). There may be mild discomfort, itching, redness, bruising, inflammation, or hyper-/hypopigmentation, and infection at the treatment sites or where adhesives were in contact with the skin. Loss of confidentiality is also a risk.

### **VIII.2**

*What have you done to minimize the risks?*

- *If applicable to this study ALSO include:*
  - *How you (members of your research team at Iowa) will monitor the safety of individual subjects.*
  - *Include a description of the availability of medical or psychological resources that subjects might require as a consequence of participating in this research and how referral will occur if necessary (e.g. availability of emergency medical care, psychological counseling, etc.)*

During the consent process the subjects will be counseled about the micropatch. The skin will be cleansed thoroughly with alcohol wipes prior to applying the micropatch treatments (cleaning technique similar to that used for insertion of a typical hypodermic needle). They will also be counseled about the possibility of local skin irritation and redness from the adhesive tape. Subjects will be closely observed during the measurements and during treatment with the micropatches. Subjects will be instructed to contact a member of the study team if problems arise at any time during their participation in the study (all pertinent contact information will be provided to the subjects). Within 3 -4 days following study completion, a member of the research team will call or email the subject to follow-up and be sure that no irritation or infection has occurred. The risk of loss of confidentiality will be minimized by keeping all documents in a locked cabinet that is only accessible to members of the research team. All electronic forms of data will be kept on a secure-server supported by the University of Iowa that allows only members of the research team access.

### **VIII.3**

*Does this study have a plan to have an individual or committee review combined data from all subjects on a periodic basis (such as summary or aggregate safety and/or efficacy data)?*

No

## IX. Benefits

**IX.1**

***What are the direct benefits to the subject (do not include compensation or hypothesized results)?***

There are no direct benefits to the subjects.

**IX.2**

***What are the potential benefits to society in terms of knowledge to be gained as a result of this project?***

Microneedle assisted transdermal delivery shows promise as an alternative to hypodermic needles. While there are increasing numbers of studies involving microneedles, differences in micropore closure kinetics among racial/ethnic groups are lacking. In addition, the use of OCT as a noninvasive skin imaging technique to view the micropores in the skin shows promise but has not been studied in different racial/ethnic groups.

## X. Privacy & Confidentiality

**X.1**

***What are you doing to protect the **privacy** interests of the subjects?***

No direct patient identifiers will be recorded on data collection material. Instead, subjects will be assigned a subject number on study materials. Only the data necessary to answer the research questions will be collected, and all in person consent processes and study procedures will take place in a private location in the College of Pharmacy building.

**X.2**

***Are you collecting the Social Security Number of any subjects for any purpose?***

Yes

**X.3**

***Provide the intended usage of SSN:***

- To provide compensation to subjects

**X.4**

***How will information/data be collected and stored for this study (check all that apply):***

- Paper/hard copy records (hard copy surveys, questionnaires, case report forms, pictures, etc.) - Paper/hard copy documents will only be transported, transferred, and stored by study team members. These documents will be stored in a secure filing cabinet in a locked office in the College of Pharmacy office 558. This office is shared with people outside of the research study team, but the lock on the cabinet is only available to those on the study team.
- Electronic records (computer files, electronic databases, etc.) - Electronic Records are stored on a secure Shared rdss drive within the university of iowa drives. This drive is access is managed by the Principle Investigator and permission is only permitted to those on the study team.
  - Name - [name]
  - Title - IT Director
  - University Job Classification - Faculty/Staff

**X.5** *Do the confidentiality protections indicated above allow only members of the research team to access the data/specimens?*  
Yes

**X.7** *Does your study meet the NIH criteria for a [Certificate of Confidentiality](#) or will you be applying for Certificate of Confidentiality?*  
No

## **XI. Data Analysis**

**XI.1** *Describe the analysis methods you will use, including, if applicable, the variables you will analyze*  
Paired t-tests will be performed to compare impedance and TEWL measurements pre- and post-micropatch treatment at each site. Influence of skin color and self-reported ethnicity/race on measured parameters will be compared using one-way ANOVA. Micropore closure kinetics will be calculated by modeling the data and calculating a micropore closure half-life. Epidermal thickness, skin roughness, and microvasculature density will be calculated by the OCT software and compared between groups using one-way ANOVA. For all analyses,  $p < 0.05$  will be considered statistically significant. GraphPad Prism Software (GraphPad Software, San Diego, CA) or Microsoft Excel will be used for statistical analyses.

**XI.2** *Provide the rationale or power analysis to support the number of subjects proposed to complete this study.*  
This is a pilot study that does not require a power analysis because data regarding the variability in parameters measured via OCT in racial/ethnic groups is not available. We are targeting 20 subjects per group because this is a reasonable number of subjects for a pilot.

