## Project Details

### I. Project Introduction

**I.1** *Project to be reviewed by:*  
IRB-01

**I.2** *Project Title:*  
Evaluating racial and ethnic differences in micropore closure using optical coherence tomography

**I.3** *Short Title (optional):*  
Visualizing micropore closure with OCT

**I.4** *Provide a short summary of the purpose and procedures of the study proposed in this IRB application.*

- ***DO NOT include information on studies not proposed in this application.***
- ***Use LAY terminology only. This must be easily understandable by IRB community members and nonscientists.***
- ***DO NOT cut and paste technical abstracts from funding applications that may not be understood by a general audience.***

The purpose of this study is to use an innovative, noninvasive imaging technique called optical coherence tomography (OCT) to visualize micropore closure in racial/ethnic skin following micropatch application. Healthy and consenting adult volunteers (18-45 years old) will be enrolled. Subjects will be asked to self-identify their race and ethnicity according to the following groups: Black, Asian, Latinx, White, Indigenous, or Bi-/multi-racial/other. All subjects, regardless of self-identified race/ethnicity, will receive the same micropatch treatment and measurements. The micropatches are patches containing a small array of microneedles on an adhesive patch backing; the whole micropatch fits on the tip of a thumb. The micropatches will be applied to the upper arm, forearm, and the palm. At each of these locations, 3 sites will be identified. One site will receive micropatch application followed by occlusion with a small patch (note: this is just a band-aid like patch, not a micropatch). The other 2 sites will be controls: one site will be treated with a micropatch but will not be covered afterwards, and the other site will be an occlusion control site (covered with an occlusive patch but no micropatch application). Noninvasive measurements will be made at baseline to determine

differences in hydration, skin water loss, electrical resistance (impedance), and color between subject groups. OCT scans will be made on the skin to noninvasively visualize the skin structure, allowing calculations of epidermal thickness and microvasculature density. After the micropatch is applied to one site at each of the 3 body locations, the water loss, impedance, and OCT measurements will be repeated. The micropatches are only applied on the first study day.

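### One-way ANOVA in XI.1 leaves the unit of analysis undefined for 9 correlated sites per subject, cannot test group differences across locations, and forces quantitative skin color into undefined categories

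*Combined protocol and SAP*

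**What the plan says.** Section XI.1 is the only statement of the analysis; VII.B.11 confirms that there is no separate protocol. It assigns one-way ANOVA twice. The first use is general: "Influence of skin color and self-reported ethnicity/race on measured parameters will be compared using one-way ANOVA". The second is for epidermal thickness, skin roughness and microvasculature density from OCT, compared between groups. The threshold is p < 0.05 throughout.

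A site-level unit appears only for the pre/post comparison: "Paired t-tests will be performed to compare impedance and TEWL measurements pre- and post-micropatch treatment at each site". For the closure outcome the plan says "Micropore closure kinetics will be calculated by modeling the data and calculating a micropore closure half-life", with no test explicitly attached to the result.

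The data structure is in VII.E.6: three sites on each of the palm, forearm and upper arm, with three different site treatments at each location. After the baseline measurements, "TEWL, Dynamic-OCT, and impedance measurements will be repeated immediately after micropatch application" and "Dynamic-OCT and impedance measurements will be measured at all sites on days 1 and 2". For color, "Skin color and redness will be measured by placing a colorimetry probe gently against each site", at baseline only. TEWL is measured on Day 0 only.

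I.4 says that baseline measurements serve to determine "differences in hydration, skin water loss, electrical resistance (impedance), and color between subject groups". The aim in I.5 is closure rates at three anatomical sites in different racial/ethnic groups. I.6 describes colorimetry as quantitative and ranks it above self-reported race as an indicator of skin variability.

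**The concern.** Neither ANOVA sentence says whether one observation is a subject, a location or a site, and no averaging rule appears elsewhere. For OCT variables and for anything measured after application, the time is not stated either. The same data could therefore give several unranked tests per parameter or one subject-level test that ignores location, and the choice could be made after the results are seen.

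Location is part of the aim, but one-way ANOVA has a single factor. Whether groups differ more at one location than at another is a natural question for this design, though not a stated hypothesis. The planned method can approach it only by comparing p-values across separate tests, which is unreliable.

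Skin color is the sharpest case. By the sponsor's own account it is the better predictor, yet it is given a method that needs categories. With no cut points defined, the plan risks losing power and leaves a choice that can be steered by the data.

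**Working it through.** **Inputs from the documents.** 9 sites per subject (VII.E.6); 20 subjects per group (XI.2); 100 enrolled (VI.1); alpha 0.05 (XI.1). XI.2 gives no power, effect size or SD, so there is no power calculation to reproduce. The number of groups is inferred: 100 / 20 = 5. I.4 lists six categories, and 6 × 20 = 120 does not match 100. Five groups are assumed below.

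**Values per subject, OCT and impedance.** Baseline 9, after application 6 (micropatch sites only), Days 1 and 2 together 2 × 9 = 18. Total 9 + 6 + 18 = 33 site-time values per variable. TEWL has two times and color one.

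**Each single test.** With one value per subject, the ANOVA has 5 − 1 = 4 and 100 − 5 = 95 degrees of freedom and keeps its 5% error. This holds for one site, one location or a subject average.

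**Several unadjusted tests of one parameter at one time.** If the tests were independent, the chance of any false positive is 1 − 0.95^m: for m = 3 locations, 1 − 0.95³ = 14.3%; for m = 9 sites, 1 − 0.95⁹ = 37.0%. Sites on one person are correlated, and the documents give no correlation, so a range is assumed (simulation, 20,000 replicates):

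| Assumed correlation | 3 locations | 9 sites |
|---|---|---|
| 0.3 | 13.5% | 33.0% |
| 0.5 | 12.5% | 28.9% |
| 0.7 | 11.0% | 21.6% |

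**Reading location differences from separate tests.** Suppose that the group difference is identical at all three locations (an assumed linear trend over groups, correlation 0.3 to 0.7). The three tests still disagree, some below 0.05 and some not, in 63% down to 41% of studies when each test has 50% power, and in 42% down to 28% when each has 80%. Such a pattern says nothing about location, and one-way ANOVA has no interaction term to settle the matter.

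**Skin color.** Assumptions: normal predictor, linear relation, N = 100, correlation 0.275 (chosen so that the continuous analysis has 80% power), equal-sized categories, one value per subject (20,000 replicates):

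| Analysis | Power |
|---|---|
| Continuous | 80.0% |
| 2 categories | 60.3% |
| 3 categories | 59.0% |
| 4 categories | 56.0% |
| 5 categories | 52.8% |
| 6 categories | 49.5% |

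With no true relation, taking the smallest p-value over 2 to 6 categories falls below 0.05 in 14.6% of studies.

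**The case against.** The best defence is that this is a self-described pilot, that each sensible reading of the ANOVA keeps 5%, and that one sentence naming unit, location and time would close most of the gap. Much of this stands. The pilot label in XI.2 explains the missing power analysis, and exploratory tests need no formal multiplicity control if labelled as such. But XI.1 applies a significance threshold to every analysis without such a label. A sentence on the unit would also leave untouched both the group-by-location question and the color categories.

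The time point is also less open than the ANOVA sentences alone suggest. I.4 ties the group comparisons of hydration, water loss, impedance and color to baseline. The gap in timing is limited to the OCT and post-application comparisons.

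The skin-color loss depends on a roughly linear relation; with a strongly curved one, categories could do better than a straight line. That limits the figure and is a reason to check for curvature, but it does not justify undefined cut points.

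A reader might go further in two ways that the documents do not support:

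- **Pooled sites.** One might infer that all sites will be entered as independent observations. The plan neither says nor excludes this. The error rate would then depend on unknown correlations and on differences between locations and treatments, so neither its size nor its direction can be given.
- **Sex, age and BMI.** These are collected but not used in XI.1, and the answer to "Will subjects be randomized" is no. One might infer that chance imbalance makes the ANOVA invalid. It does not: with sex distributed at random over five groups of 20 and assumed sex effects of 0 to 1.2 SD, the unadjusted test rejects in 4.8-5.1% of studies. Only systematic differences from recruitment would bias a comparison, and the documents give no basis for sizing them.

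**Conclusion.** The concern holds as a weakness in the choice of analysis that is cheap to correct. It is not a demonstrated error in the test level. The unit of analysis and the handling of locations are unstated for every ANOVA, and the time is unstated for the OCT and post-application comparisons. The method cannot address variation of group differences across the three locations in the aim. Unadjusted testing at three locations carries about an 11-14% chance of any false positive per parameter and time, under an assumed correlation of 0.7 to 0.3 and five inferred groups of 20.

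For skin color, the stated method does not suit a quantitative measurement. The fall from 80% to about 50-60% power assumes linearity, a normal predictor and equal-sized categories. The rise from 5% to about 15% assumes that the number of categories, from 2 to 6, is chosen after seeing the data. The plan should be changed before analysis.

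**What to change.** In XI.1:

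1. **Skin color.** Analyse the colorimetric value as a continuous predictor, by regression or in a mixed model, with a check for non-linearity, instead of one-way ANOVA.
2. **Group comparisons.** Use a linear mixed model per parameter with random effects for subject and for location within subject. Fixed effects are group, location, group by location and, for values after application, site treatment. Where several times are analysed together, add time, group by time and a subject-by-time term, and check the variance assumptions. A simpler alternative or fallback is a stated summary with one value per subject, or one per subject and location. The single value per subject is valid but gives up the location question.
3. **Main comparison.** Name one in advance, with its time point, and label the rest exploratory. The choice is the sponsor's; log closure half-life at the micropatch sites, by group across locations, would be one candidate.

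Analyses adjusted for age, sex and BMI are an optional sensitivity analysis, because non-randomised groups may differ systematically.

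The cost is revised wording, some extra analysis work and possibly software other than the two packages named in XI.1. The results would rely on mixed-model and linearity assumptions, which need checking. No new data or visits are needed.
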